16.2.2.2 Food Effect

The effect of food and the timing of food will be graphically presented using box-plots showing AUC_{0-24} , C_{max} versus treatment. This will be done in separate plots for the following comparisons:

- 100 mg LY fasted, 100 mg LY QD (Day only), 100 mg LY fed (-30 min), 100 mg LY fed (+30 min), and 100 mg LY fed (+60 min)
- 30 mg LY fasted (Cohort 6 Period 1) and 30 mg LY fed (Cohort 3 Period 2)
- 200 mg LY fasted 200 mg LY fed (Cohort 4 Periods 1 and 2)

In addition, for the 200 mg dose level (i.e. Cohort 4 Periods 1 and 2), an analysis of variance (ANOVA) will be performed on AUC_{0-24} and C_{max} using the SAS PROC MIXED to estimate the geometric mean ratio and corresponding 90% CIs. Dose normalized PK parameters will be natural logarithm transformed prior to the analysis. The model will include fixed effects for food consumption status (fasted or fed) and a random effect for subject. From this model the back-transformed least-squares means (LSMeans) for each treatment and their ratio will be estimated. The ratio of least-squares geometric means between fed and fasted condition and the corresponding 90% CI will be presented.

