- ⁱ On Day 1, PK samples will be collected at time zero (predose) and at approximately 1, 2, 4, 6, 8, and 12 hours after dosing. One PK sample will be taken at 24 and 48 hours postdose (Days 2 and 3), and if applicable, at the ED Visit. PK sample collection times are provided as a guidance and may be modified based on clinical needs. Actual dates and times of sample collection must be recorded. The following time collection intervals are proposed: predose samples may be obtained between waking up and dosing. Postdose samples may be obtained within $\pm 5\%$ of the scheduled collection time. The $\pm 5\%$ time window also applies to the start and end times of urine collection intervals. Post-assay remainder PK plasma samples may be stored for metabolite identification.
- ^j Urine collection interval is 0 to 24 hours postdose. The total urine volume of the 0- to 24-hour collection will be recorded.

Table 2-2 **Study Schedule Protocol J2D-MC-CVAA: Part A Cohort 10**
(3-Period Food Effect Cohort)

	S	Treatment/ In CRU					Posttreatment	ED ^a
Study Day (visit window)	≤ 28	-1	1	2	3	4	10 (± 2)	
Period		1-3					3	1-3
Visits	1 ^b	2 ^c					3	
CRU admission		X						
CRU discharge						X		
Participant information (including I/E criteria)	X	X						
Informed consent	X							
Medical history	X							
Height	X							
Weight	X		X				X	X
Physical examination (complete [C] or directed [D])	C	D	D	D	D	D	C	C
Urine drug screen and ethanol test	X	X						
Vital signs including temperature	X	X	X (predose, 2 h, 4 h, 8 h)	X	X		X	X
Hematology and clinical chemistry	X	X		X ^d	X ^d		X	X
Urinalysis ^e	X	X						
Pregnancy test (serum beta-hCG) ^f	X	X					X	X
HIV, HCV, HBsAg	X							
ECG ^g		X	X (predose, 2 h, 4 h, 8 h)				X	X
C-SSRS	X	X					X	X
Randomization			X ^h					
Study drug administration ⁱ			X					
PK blood sample ^j			X	X	X	X		X
PK 24-hour urine collection ^k			↔ X →					
Adverse event				↔ X →				
Concomitant medications				↔ X →				

Abbreviations: C = complete physical examination; CRU = clinical research unit; C-SSRS= Columbia-Suicide Severity Rating Scale; D = directed physical examination; ECG = electrocardiogram; ED = early discontinuation; h = hour; HBsAg = hepatitis B surface antigen; hCG = human chorionic gonadotropin; HCV = hepatitis C virus; HIV = human immunodeficiency virus; I/E = inclusion/exclusion; PK = pharmacokinetics; S = screening; SAD = single-ascending dose.

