^a Participants who discontinue from the study prior to study completion should complete the ED visit procedures.

^b Screening will be performed within 28 days of the first dose being administered.

^c All participants will remain in the CRU until completion of Day 4 procedures.

^d Hematology and clinical chemistry sample to be taken in the morning.

^e A standard urine test strip/dipstick may be used.

^f A serum beta-hCG test will be performed in all female participants, except in female participants with confirmed hysterectomy.

^g A single 12-lead ECG will be recorded in the supine position after 5 minutes of rest.

^h randomization will occur during first period only.

ⁱ Doses are planned to be administered as follows in each period:

- Period 1-Fed standardized high fat meal to start 30 minutes prior to dose administration
- Period 2-Fasted at least 8-hours predose with a standardized high fat meal administered 30 minutes post dose
- Period 3-Fasted at least 8-hours predose with a standardized high fat meal administered 1 hour post dose

Periods will be separated by a washout of at least 1 week. The meals administered in all treatment periods should be consumed within 30 minutes. The exact time study drug is administered will be recorded.

^j In each treatment period, on Day 1, PK samples will be collected at time zero (predose) and at approximately 1, 2, 4, 6, 8, and 12 hours after dosing. One PK sample will be taken at 24, 48, and 72 hours postdose (Days 2, 3, and 4), and if applicable, at the ED Visit. PK sample collection times are provided as a guidance and may be modified based on clinical needs. Actual dates and times of sample collection must be recorded. The following time collection intervals are proposed: predose samples may be obtained between waking up and dosing.

Postdose samples may be obtained within $\pm 5\%$ of the scheduled collection time. The $\pm 5\%$ time window also applies to the start and end times of urine collection intervals. Post-assay remainder PK plasma samples may be stored for metabolite identification.

^k Urine collection interval is 0 to 24 hours postdose. The total urine volume of the 0- to 24-hour collection will be recorded.

Table 2-3 **Study Schedule Protocol J2D-MC-CVAA: Part B (MAD)-Cohort 7**

	S	Treatment/In CRU								Post treatment	ED ^a
		-1	1	2	3	5	8	14	15		
Study Day	≤28									23	
Visit Window (days)										±2	
Visits	1^b									3	
CRU admission		X									
CRU discharge									X		

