10.3.2.1.1 Plasma Pharmacokinetic Parameter Estimation

Part A

Primary plasma LY3526318 PK parameters, including but not limited to the area under the concentration versus time curve (AUC) from time zero to the last measurable concentration (AUC_{0-t}), AUC from time zero to 24 hours (AUC₀₋₂₄), AUC from zero to infinity (AUC_{0-inf}), maximum observed drug concentration (C_{max}), and the time to C_{max} (t_{max}) will be calculated using noncompartmental methods. Other PK parameters, such as apparent t_{1/2}, apparent clearance (CL/F), and apparent volume of distribution (Vz/F) will also be calculated.

For the food effect exploration, the geometric means of the ratios of the log-transformed exposure measures (AUC, C_{max}) between the fed and fasted conditions, and the 90% confidence intervals for the ratios will be reported.

Pharmacokinetic parameters will be calculated individually and presented with summary statistics. Additional PK parameters may be calculated if deemed appropriate.

Mean and individual plasma concentration versus time curves will be graphically presented for LY3526318 and possibly metabolites.

Part B

Plasma LY3526318 PK parameters will be calculated using noncompartmental methods as described for Part A, after single- and multiple-dose administration (on Days 1 and 14, respectively). Additional PK parameters may be calculated if deemed appropriate.

Pharmacokinetic parameters will be summarized by dose level using descriptive statistics. Mean and individual plasma concentration versus time curves will be graphically presented for LY3526318 and possibly metabolites.

Steady state will be graphically evaluated. Accumulation will be estimated.

Additional analyses will be performed as deemed necessary upon review of the data.

The relationship between LY3526318 PK and safety measures may be evaluated. Other analyses may be performed as needed.

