Appendix 8. Protocol Amendment: J2D-MC-CVAA(b)

Protocol J2D-MC-CVAA has been amended; the new will be indicated as amendment (b) and will be used to conduct the study in place of any preceding version of the protocol.

The overall changes and rationale for the changes made to this protocol are as follows:

Section	Changes made	Rationale for the change
2. Study Schedule Protocol J2D-MC-CVAA: Part B (MAD) and associated text throughout protocol	Two additional SOE tables for Cohorts 8 and 9 to clearly indicate differing in house stays for additional PK sample collection regimens between the MAD cohorts. For Cohorts 8 and 9, the revised PK sample collection schedule runs through 96 and 120 hours post Day 14 dose, respectively, with only 3 PK samples added in each cohort.	SAD PK data resulted in a longer half-life than was predicted, so additional collections required to characterize the terminal elimination of LY3526318
2. Study Schedule Protocol J2D-MC-CVAA: Part B (MAD)	Temperature timepoints revised to be consistent with Vital Sign timepoints	Administrative update
Appendix 5. Blood Sampling Summary	Revised blood volume based on additional PK samples	Same as above.
7.1 Treatment Administered	Revised the capsule strengths from “10 mg and 100 mg” to “10 mg to 100mg”	Capsules will be prepared at dosage strengths administered.

Revised Protocol Sections

Note: Deletions have been identified by ~~strike-throughs~~ or grayed out for figures. Additions have been identified by the use of underscore.

2 Schedule of Activities

Study Schedule Protocol J2D-MC-CVAA: Part B (MAD)-Cohort 7

	S	Treatment/In CRU								Post treatment	ED ^a
Study Day	≤28	-1	1	2	3	5	8	14	15	23	
Visit Window (days)										±2	
Visits	1 ^b	2								3	
CRU admission		X									
CRU discharge									X		
Participant information (including I/E criteria)	X	X									
Informed consent	X										
Medical history	X										
Height	X										
Weight	X		X							X	X
Physical examination (complete [C] or directed [D])	C	D	D	D	D	D	D	D		C	C
Urine drug screen and ethanol test	X	X									
Vital signs including temperature ^c	X	X	X	X	X	X	X	X		X	X
Hematology and clinical chemistry ^d	X	X		X			X	X		X	X
Urinalysis ^e	X	X									
Pregnancy test (serum beta-hCG) ^f	X	X								X	X
HIV, HCV, HBsAg	X										
ECG ^g	X		X					X		X	X
C-SSRS	X	X							X	X	X
Randomization			X								
Study drug administration ^h					← X →						
PK blood sample ⁱ			X	X	X	X	X	X	X		X
Adverse event					← X →						

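### The 200 mg food-effect ratio and all food box plots stop at AUC0-24, which can understate fed exposure if food delays absorption; AUC0-48 from samples already scheduled would largely remove this

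*SAP*

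**What the plan says.** SAP 16.2.2.2 handles food in two ways.

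- **Graphs.** "The effect of food and the timing of food will be graphically presented using box-plots", drawn for AUC0-24 and Cmax. The three plots are 30 mg (Cohort 6 fasted, Cohort 3 Period 2 fed), 200 mg (Cohort 4, both periods) and 100 mg (fasted, three meal timings, and the once-daily 100 mg arm).
- **Model.** Only Cohort 4 is modelled: "an analysis of variance (ANOVA) will be performed on AUC_{0-24} and C_{max} using the SAS PROC MIXED". "The ratio of least-squares geometric means between fed and fasted condition and the corresponding 90% CI will be presented".

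Related text elsewhere:

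- Protocol 10.3.2.1.1 names AUC0-t, AUC0-24 and AUC0-inf. For food it then promises "the geometric means of the ratios of the log-transformed exposure measures" (AUC and Cmax) with 90% intervals, without saying which AUC. Protocol Table 4-1 lists AUC, Cmax and tmax for the fed-versus-fasted objective.
- Protocol 5.5 relied on a monkey half-life of 2 to 4 h. The amendment (b) rationale in Appendix 8 states: "SAD PK data resulted in a longer half-life than was predicted, so additional collections required to characterize the terminal elimination of LY3526318".
- Sampling runs to 48 h in Cohorts 1-6 (Protocol Table 2-1, footnote i) and to 72 h in each Cohort 10 period (Table 2-2, footnote j).
- SAP Table 6 computes AUC0-last and AUC0-inf for single doses, and calls AUC0-inf reliable when at most 20% is extrapolated.
- SAP 16.2.2.1 uses AUC0-inf first for single-dose proportionality, with AUC0-24 as the fallback.

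**The concern.** A fed/fasted AUC ratio is normally read as a statement about extent of absorption. A 24 h partial AUC measures extent only if nearly all exposure falls inside the window in both conditions. When the half-life is not short and a meal slows absorption, more of the fed curve than of the fasted curve lies after 24 h, so the AUC0-24 ratio mixes rate with extent.

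The plan's own record makes this worth guarding against. The half-life exceeded the prediction, and Part B sampling was extended for that reason. The food section gives no reason for stopping at 24 h, while the section next to it prefers AUC0-inf.

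Protocol 5.4 says the food assessment is to inform how the drug is given in the MAD and later studies. Cohort 10 compares meal timings, where differing delay is a plausible difference between arms and could look like a difference in exposure.

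**Working it through.** The documents give no figure to reproduce here: no human half-life, no delay and no within-subject variability. The calculation below is an illustration.

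**Assumptions (not from the documents).** One compartment, first-order absorption, equal bioavailability, so the true fed/fasted ratio is 1.00. Fasted ka is 1/h with no lag. Fed ka is 0.5 to 0.2/h with a lag of 1 to 2 h. Half-life is 4 h (the top of the monkey range, for reference), 6, 12 or 24 h.

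**Formula.** With ke = ln 2 / half-life, x = T − lag, and dose × F / V set to 1:

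AUC(0-T) = ka/(ka − ke) × [(1 − e^(−ke·x))/ke − (1 − e^(−ka·x))/ka]

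**One case in full: half-life 12 h, fed ka 0.2/h, lag 2 h.** ke = 0.05776.

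- Fasted, T = 24: 1.0613 × [0.75/0.05776 − 1.000] = 1.0613 × 11.984 = 12.72.
- Fed, x = 22: 1.4061 × [0.7194/0.05776 − 0.9877/0.2] = 1.4061 × 7.516 = 10.57.
- AUC0-24 ratio = 10.57/12.72 = 0.831, a shortfall of 17% with no change in extent.
- The same steps to 48 h give 15.61/16.16 = 0.965, a shortfall of about 4%.

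**All cases.** Each range runs from the mildest delay (ka 0.5/h, lag 1 h) to the most marked (ka 0.2/h, lag 2 h).

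| Half-life | Share of fasted total AUC within 24 h | AUC0-24 ratio | AUC0-48 ratio | AUC0-72 ratio (Cohort 10 only) |
|---|---|---|---|---|
| 4 h | 98% | 0.99-0.93 | 1.00 | 1.00 |
| 6 h | 93% | 0.98-0.89 | 1.00-0.99 | 1.00 |
| 12 h | 73% | 0.95-0.83 | 0.99-0.96 | 1.00-0.99 |
| 24 h | 49% | 0.93-0.79 | 0.98-0.93 | 0.99-0.97 |

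The AUC0-24 shortfall is about 2-11% at 6 h, 5-17% at 12 h and 7-21% at 24 h. On AUC0-48 it is about 1% or less, 1-4% and 2-7%. These delays move tmax from 3.0 h fasted to 5.9-10.7 h fed at a 12 h half-life, and from 3.6 h to 7.1-13.3 h at 24 h. A pure 2 h lag with unchanged ka costs only about 4% (12 h) or 6% (24 h) on AUC0-24.

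**If food truly raises exposure.** Protocol 5.5 expects about a 3- to 5-fold rise with a high-fat meal. Multiplying by the ratios above at half-lives of 12-24 h, a true 3 would show as about 2.4-2.9 and a true 5 as about 3.9-4.8. The ratio remains well above 1.

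**Would AUC0-inf do instead?** Noncompartmental analysis on the protocol's 48 h sampling grid, with fed delays of ka 0.25 to 1/h and a lag of 2 to 4 h, extrapolates 7-12% at a 12 h half-life. At 24 h it extrapolates 26-36%, beyond the SAP's 20% limit. AUC0-inf is therefore least reliable where the 24 h cut costs most.

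**The case against.** The strongest reply is that the other measures are not lost. SAP 16.2.2 summarises the Table 6 parameters by treatment, and each fed condition is its own treatment (SAP Table 3). The Appendix 4 shell sets fed and fasted columns side by side with AUC0-inf, tmax and half-life. SAP 16.2.1 plots mean profiles fed against fasted at 30 and 200 mg, and by meal timing at 100 mg. A delayed peak would be visible there. This stands, and it narrows the point: what is missing is a fed/fasted ratio with an interval, and a graphical comparison, on a window longer than 24 h.

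A reader might infer that a delayed fed peak will be reported as lower exposure. The documents do not support that. It would need a long half-life, a material delay and almost no change in extent, whereas the protocol expects a large rise.

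A reader might also infer a departure from the protocol. That does not follow: the protocol says only AUC for the food ratios, and AUC0-24 is among the parameters it names.

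Precision limits the point too. Cohort 4 has about 6 active participants. Under an assumed within-subject CV of 20-30%, the 90% interval is the estimate multiplied or divided by exp(2.015 × s × √(2/6)), with s = √ln(1 + CV²), that is by 1.26 to 1.41. Every shortfall in the table up to a 12 h half-life fits inside that. A systematic shift in a reported ratio is still worth removing when the data are already in hand.

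Finally, AUC0-24 is the right window in one place. The 100 mg box plot includes the once-daily 100 mg arm, apparently Day 1 (the SAP label omits the day number), where the next dose ends the interval at 24 h.

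**Conclusion.** The point holds in a limited form. The only fed/fasted ratio and every food box plot use AUC0-24 and Cmax, no reason is given, and the plan has both evidence of a longer half-life and samples beyond 24 h. If food delays absorption, the AUC0-24 ratio can understate fed extent. In the illustration the shortfall is at most 7% at a 4 h half-life and reaches 21% at 24 h with the most marked delay; AUC0-48 removes most of it.

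The direction follows whenever absorption is delayed and exposure continues past 24 h. The size rests entirely on the assumed half-life and delay. With a 3- to 5-fold food effect the consequence is an understated increase. The analysis is exploratory, unpowered and has no food-effect acceptance limits, so this is an inexpensive improvement and does not invalidate the plan.

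**What to change.** In SAP 16.2.2.2:

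- Add AUC0-48 to the 200 mg fed/fasted model as the measure of extent, and report its ratio with the 90% interval. It is the longest window scheduled in all single-dose food arms.
- Add AUC0-inf as a further measure when extrapolation is at most 20% in both periods for most participants.
- Add AUC0-48 to the single-dose box plots: 30 mg, 200 mg, and 100 mg without the once-daily arm.
- Add AUC0-72 for comparisons within Cohort 10 only, because the 100 mg fasted reference stops at 48 h.
- Keep AUC0-24 and Cmax throughout, with AUC0-24 the only AUC for the once-daily 100 mg arm on Day 1.
- Refer the reader to the tmax summaries already planned, so that delay and extent are read together.

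The cost is SAP wording and one extra AUC window (two in Cohort 10), with no new sampling. AUC0-48 is lost for a participant who misses the 48 h sample. Since SAP 16.2.2 treats late values below quantification as missing, the text should also say how AUC0-48 is obtained when the 48 h value is not quantifiable.

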16.2.3 Pharmacokinetic Amounts Excreted

The volumes of the urine 0-24h collection intervals and the concentrations measured in these intervals as well as the start and end times of the urine collection and the derived amounts excreted in each interval will be listed by subject.

Descriptive statistics (number of subjects, arithmetic mean, standard deviation, coefficient of variation, median, minimum, and maximum) will be used to summarize the amounts of LY3526318 excreted in urine.

17.0 Pharmacodynamic and Biomarker Analysis

Not applicable.

18.0 Safety Analyses

18.1 Safety Variables

The following safety variables will be summarized:

- AEs
- Vital Signs (measurement after 5 minutes of rest in supine position)
 - Supine Blood Pressure
 - Systolic Blood Pressure (SBP) [mmHg]
 - Diastolic Blood Pressure (DBP) [mmHg]
 - Pulse rate [bpm]
 - Oral body temperature [C]
 - Body Weight [kg]
- Electrocardiogram (ECG) parameters (measurement after 5 minutes of rest in supine position)
 - Heart Rate [bpm]
 - PR-Interval [ms]
 - QRS-Duration [ms]
 - QT-Interval [ms]
 - QTc Fridericia [ms]
- Clinical Laboratory Evaluations
 - Clinical Chemistry
 - Hematology
 - Urinalysis
- Columbia-Suicide Severity Rating Scale (C-SSRS)

18.1.1 Adverse Events

Treatment-emergent adverse events (TEAE) are those which occur after the first dose of study drug.

All AEs (including non-treatment-emergent events) will be listed, including the AE description (verbatim term), Medical Dictionary for Regulatory Activities (MedDRA) system organ class (SOC) and preferred term (PT), start date and time, end date and time, severity, relation to study drug, seriousness, action taken, and outcome.

All AE summaries will include only TEAE. All TEAEs occurring following dosing will be attributed to the treatment that was received.

A breakdown of the number of TEAEs, and the number and percentage of subjects reporting each TEAE, categorized by system organ class and preferred term coded according to MedDRA (Version 22.1), will be presented by treatment and overall for each study part. One table is presented for all TEAEs and one table is presented for TEAEs considered to be related to the study medication. Subjects will only be counted once within each SOC or PT per treatment.

Additionally, a summary table with TEAEs by severity and relationship to study drug will be presented by study part and treatment.

The following missing data will be imputed as defined (for calculations only / will not be presented):

- Missing AE start and / or end times for the calculation of onset and duration will be assumed to be at 00:01 for a start time and 23:59 for end times
- Missing AE severity or relationship will be assumed to be severe or related, respectively
- Missing AE start times for the determination of treatment emergence will be assumed to occur after treatment unless partial date documents the AE as happening prior to treatment
- Missing AE start times for the determination of treatment assignment will be assumed to occur after treatment on the recorded date
- Missing AE start date will be assumed to be after treatment for the determination of TEAE and on treatment

For the US Clinical Trials Registry (CTR), a CTRAE summary table and the CTRAESUMM SAS dataset will be provided separately from the TFL created for CSR. The table and corresponding dataset will be created according to the specifications provided by the Sponsor.

